5.3 Lifestyle restrictions

There are no lifestyle restrictions during the study unless deemed to interfere with compliance with the protocol as deemed by the Investigator.

The use of medicinal cannabinoids and medicinal marijuana (prescribed by a Physician) is permitted. For Japan-specific regulations, see Appendix 8 (Section 10.8).

5.4 Screen failures

Applicable to study participants with a gap period only (see Section 10.11).

Screen failures are defined as participants who consent to participate in the clinical study but are not subsequently entered in the study. A minimal set of screen failure information is required to ensure transparent reporting of screen failure participants to meet the Consolidated Standards of Reporting Trials (CONSORT) publishing requirements and to respond to queries from regulatory authorities. Minimal information includes demography, screen failure details, eligibility criteria, and any serious adverse event (SAE).

For study participants otherwise fully eligible but not able to enter the study as planned for nonclinical reasons, rescreening may be allowed at the discretion of the Investigator, following discussion with the sponsor's Medical Monitor and/or Study Physician.

If a study participant has 1 isolated test result in the exclusionary range that is deemed not being clinically significant by the Investigator, retesting may be allowed at the discretion of the Investigator, following discussion with the sponsor's Medical Monitor and/or Study Physician. If the normalization of the test result occurs within the Screening Period, then no other screening procedures need to be repeated.

6 STUDY TREATMENTS

Study treatment is defined as any investigational treatment(s), intended to be administered to a study participant according to the study protocol.

6.1 Treatments administered

A description of the IMP to be administered in MG0007 is provided in [Table 6-1](#).

Table 6-1: Study treatments administered

Intervention name	Rozanolixizumab
Type	Drug
Dose formulation	Solution for injection A glass vial, containing rozanolixizumab at a concentration of [REDACTED] [REDACTED]
Dosage level(s)	See Table 6-2
Route of administration	Subcutaneous infusion via syringe driver or manual push method
Use	Experimental
IMP and NIMP	IMP
Sourcing	Provided centrally by the Sponsor or locally by the study site, subsidiary, or designee
Packaging and labelling	Rozanolixizumab is manufactured, packaged, and labeled according to Good Manufacturing Practice guidelines and applicable laws or regulations
Current/Former name(s) or alias(es)	UCB7665

IMP=investigational medicinal product; NIMP=non investigational medicinal product

Details on the preparation of study treatment for infusion, rate of infusion, administration, appropriate records handling, and site personnel roles are provided in the IMP Handling Manual. The optional onsite manual push route of administration performed by a healthcare professional should only be introduced at the beginning of a treatment cycle and may be reverted back to the standard syringe driver administration at any time. All site personnel delegated to handle study treatment storage, preparation and administration must be trained to IMP Handling Manual.

Rozanolixizumab sc doses across body weight tiers to be used in MG0007 are presented in [Table 6-2](#).

Table 6-2: MG0007 dose levels and weight tiers

Bodyweight	Rozanolixizumab dose eqv	
	7mg/kg Dose 1	10mg/kg Dose 2
≥35 to <50kg	280mg	420mg
≥50 to <70kg	420mg	560mg
≥70 to <100kg	560mg	840mg
≥100kg	840mg	1120mg

eqv=equivalent

6.2 Preparation, handling, storage, and accountability requirements

The Investigator or designee must confirm appropriate temperature conditions have been maintained during transit for all study treatment received and any discrepancies are reported and resolved before use of the study treatment.

Only participants enrolled in the study may receive study treatment and only authorized site staff may supply or administer study treatment. All study treatments must be stored in a secure, environmentally controlled, and monitored (manual or automated) area in accordance with the labeled storage conditions with access limited to the Investigator and authorized site staff.

The Investigator, institution, or the head of the medical institution (where applicable) is responsible for study treatment accountability, reconciliation, and record maintenance (ie, receipt, reconciliation, and final disposition records).

In case an out-of-range temperature is noted, it must be immediately reported as per instructions contained in the IMP Handling Manual.

Further guidance and information for the final disposition of unused study treatment are provided in the IMP Handling Manual.

6.2.1 Drug accountability

A Drug Accountability form will be used to record study medication dispensing and return information on a by-participant basis and will serve as source documentation during the course of the study. Details of any study medication lost, damaged (due to breakage or wastage), not used, partially used, disposed of at the study site, or returned to the Sponsor or designee must

also be recorded on the appropriate forms. All supplies and pharmacy documentation must be made available throughout the study for UCB (or designee) to review.

The Investigator (or designee) is responsible for retaining all used, unused, and partially used containers of study medication until returned or destroyed.

The Investigator may assign some of the Investigator's duties for drug accountability at the study site to an appropriate pharmacist/designee.

The Investigator must ensure that the study medication is used only in accordance with the protocol.

Periodically, and/or after completion of the clinical phase of the study, all used (including empty containers)/partially used, unused, damaged, and/or expired study medication must be reconciled and either destroyed at the site according to local laws, regulations, and UCB and/or site SOPs or returned to UCB (or designee). Investigational medicinal product intended for the study cannot be used for any other purpose than that described in this protocol.

6.3 Measures to minimize bias: randomization and blinding

An interactive response technology (IRT) will be used for assigning eligible participants to a treatment regimen (as applicable) based on a predetermined production randomization and/or packaging schedule provided by UCB (or designee). The randomization schedule will be produced by the IRT vendor. The IRT will generate individual assignments for kits of study medication, as appropriate, according to the visit schedule. Study participants from MG0003 who complete the EOS visit will be rerandomized in MG0007. Randomization in MG0007 is to a ratio of 1:1. Study participants from MG0004 will not be rerandomized upon entering MG0007, but will continue their last treatment regimen received in MG0004 for their first treatment cycle in MG0007.

To enroll a study participant (Visit 1), the Investigator or designee will contact the IRT and provide brief details about the participant to be enrolled. Study participants will retain the same 5-digit number assigned at Screening in MG0003 that serves as the participant identifier throughout the study. The participant number will be required in all communication between the Investigator or designee and the IRT regarding a particular participant. Participant numbers and kit numbers will be tracked via the IRT.

6.3.1 Procedures for maintaining and breaking the treatment blind

6.3.1.1 Maintenance of study treatment blind

This is an OLE study and treatment details (ie, dose arm) will not be blinded.

To maintain study integrity, IgG level will remain blinded to the study sites and the UCB study team for the first 4 weeks of the study.

6.3.1.2 Breaking the treatment blind in an emergency situation

Not applicable.

6.4 Treatment compliance

Drug accountability must be recorded on the Drug Accountability form (Section 6.2.1).

Details regarding treatment compliance are outlined in the Important Protocol Deviation Specification document.

6.5 Concomitant medication(s)/treatment(s)

6.5.1 Permitted concomitant treatments (medications and therapies)

Concomitant medications listed in [Table 6-3](#) are permitted during the study for the treatment of gMG, and dose adjustments are allowed between treatment cycles. With the exception of corticosteroids and AChE inhibitors, the dose of permitted concomitant medications should be maintained during each 6-week treatment cycle and every effort should be made to maintain a stable dose during the first 8 weeks of each Observation Period. Any violation of the permitted treatment criteria would lead to prohibited treatment and should be discussed with the Investigator, Sponsor, and Medical Monitor.

If a study participant receives a COVID-19 vaccine, the product name and date of administration(s) should be captured in the eCRF as a concomitant medication.

Table 6-3: Permitted concomitant treatments

Permitted Medications	Dose
Oral corticosteroids (eg, prednisolone)	No specific requirements
Methotrexate	≤30mg/week
Mycophenolate mofetil	≤3g/day
Cyclosporine ^a	≤5mg/kg/day for unmodified ≤4mg/kg/day for modified (microemulsion)
Azathioprine	≤3mg/kg/day
Cholinesterase inhibitors	≤600mg pyridostigmine/day
Tacrolimus ^b	≤5mg/day

^a Doses higher than listed are permissible if trough level is ≤300ng/mL.

^b If the total daily weight-based dose is >5mg, then a plasma trough level should be checked to ensure study participant is not above the recommended therapeutic range.

6.5.2 Prohibited concomitant treatments (medications and therapies)

The following concomitant medications are prohibited during the study:

- All biologics, including rituximab
- Cyclophosphamide
- Pimecrolimus
- IPP-201101 (LupuzorTM)
- Immunoabsorption
- Vinca alkaloids (vincristine, vinblastine)

Study participants can enroll in MG0007 irrespective of their background gMG medications.

If a study participant needs or takes any prohibited medication or therapy, the Investigator will (where possible) discuss with the Medical Monitor and/or the Sponsor's Study Physician and a decision will be made whether the study participant can continue in the study or be withdrawn.

6.5.3 Treatments specific to NMJ interference

Treatments could interfere with the function of the NMJ (and which therefore could impair study participants with MG), such as, but not limited to, include the following medications:

- botulinum toxin
- aminoglycoside antibiotics
- tetracycline antibiotics
- penicillamine
- magnesium

For a more detailed list please refer to the Myasthenia Gravis Foundation of America (MGFA) medication list (<https://myasthenia.org/What-is-MG/MG-Management/Cautionary-Drugs>). The benefit-risk of starting these medications should be carefully considered by the Investigator, and where possible, the Investigator will discuss with the Medical Monitor and/or sponsor's Study Physician prior to initiating therapy that can affect the NMJ.

6.5.4 Rescue medication

The study site will supply rescue therapy that will be obtained locally. Rescue therapy will be given as per standard of care and at the discretion of the Investigator. Study participants who continue to experience moderate to severe symptoms despite treatment with rozanolixizumab may be treated with the following as rescue therapy:

- IVIg
- SC Ig
- PEX, or plasmapheresis
- iv corticosteroids at a higher dose than previous oral dose

Participants who are treated with rescue therapy during the Treatment Period are not eligible to receive any further treatment with rozanolixizumab. Study participants must complete the first 8 weeks of the Observation Period after the last dose of rozanolixizumab prior to completing the EOS visit assessments, and subsequently will be withdrawn from the study (Section 4.4).

Those patients who received rescue therapy during the observation or no treatment with rozanolixizumab periods may continue in the study at the Investigator's discretion and after discussion with Medical Monitor and/or UCB Study Physician. The following cycle of rozanolixizumab should in general not start earlier than 4 weeks following the last dose of IVIg, SC Ig, or iv corticosteroids or the last PEX session, unless there is a medical reason, and an earlier treatment initiation is being considered █ for the study participant as agreed upon with the Medical Monitor and/or UCB Study physician.

The date and time of rescue medication administration as well as the name and dosage regimen of the rescue medication must be recorded.

6.6 Dose modification

Dose modifications from 10mg/kg to 7mg/kg equivalent and vice versa is permitted at the beginning of the treatment cycles at the Investigator's discretion, and if the benefit-risk remains favorable for the study participant. Recommended dose modifications from 10mg/kg to 7mg/kg equivalent due to drug-related adverse events which may include but not limited to:

- Moderate to severe headaches that are considered to be related to rozanolixizumab
- Moderate to severe GI disturbances that are considered to be related to rozanolixizumab
- Moderate to severe toxicities (\geq Grade 2 as defined by Common Terminology Criteria for Adverse Events [CTCAE], version 5.0) for which rozanolixizumab cannot be excluded as a cause
- Recurrent hypogammaglobulinemia with a serum total IgG level of <2 g/L.

6.7 Home (or Virtual) visits

During the Treatment Period, the at-home visits will be conducted by fully trained healthcare professional visiting the study participant at his or her home. Alternatively, these visits can be conducted at the site as deemed necessary by site personnel and/or the study participant. For home dosing, the same safety monitoring schedule will be followed as per onsite dosing. The home nurse will be present during the full duration of the visit. Home visits can be conducted if the following conditions are met:

- The study participant is willing to be dosed and monitored at home by a home nurse.
- The study participant has shown good acute tolerability to previous administrations of IMP (namely, he or she must have had no moderate or severe infusion reactions or other AEs that the Investigator considers could increase the risk of home administration).

The Investigator should complete a checklist to confirm that criteria for home nurse and/or self-administration have been fully evaluated.

Virtual visits will be conducted with study participants during the Observation Period and between cycles (see Schedule of Activities (Section 1.3); no treatment with rozanolixizumab) by site personnel. Alternatively, these visits can be conducted at the site as deemed necessary by site personnel and/or the study participant.

6.8 Treatment after the end of the study

Study participants who complete participation in MG0007 may have the possibility to continue receiving rozanolixizumab through a MAP if available, as indicated per the Sponsor and applicable per local regulations.

In the case of prolonged hypogammaglobulinemia after treatment discontinuation, study participants must be followed up until IgG levels return to values within the normal range or to individual Baseline values.

[figure not shown]
7 DISCONTINUATION OF STUDY MEDICATION AND PARTICIPANT DISCONTINUATION/WITHDRAWAL

7.1 Discontinuation of study medication

7.1.1 Liver chemistry stopping criteria

Discontinuation of study treatment for abnormal liver function should be considered by the Investigator when a participant meets one of the conditions outlined [Figure 7-1](#) and [Figure 7-2](#) or if the Investigator believes that it is in best interest of the participant.

[figure not shown]
Figure 7-1: Liver Chemistry Stopping Criteria and Increased Monitoring Algorithm

ALT=alanine aminotransferase; AST=aspartate aminotransferase; INR=international normalized ratio; SAE=serious adverse event; ULN=upper limit of normal.

Treatment with study medication may be continued with increased monitoring if a study participant meets one of the criteria outlined in [Figure 7-2](#).

Figure 7-2: Liver Chemistry Increased Monitoring Algorithm with Continued Study Intervention for Participants with ALT $\geq 3\times$ ULN but $<8\times$ ULN

ALT=alanine aminotransferase; AST=aspartate aminotransferase; bili=bilirubin; INR=international normalized ratio; SAE=serious adverse event; ULN=upper limit of normal

Specific assessments and follow up actions for potential drug-induced liver injury are provided in Appendix 6 (Section 10.6).

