7.1.4 Study medication permanent discontinuation criteria

Study participants **must** permanently discontinue study medication if any of the following events occur:

1. Study participant develops an illness that would interfere with his or her continued participation.
2. Study participant has new onset or recurrent neoplastic disease (except for superficial basal or squamous cell carcinoma of the skin not requiring targeted biological therapy, chemotherapy or radiation).
3. Study participant experiences a significant infective episode including but not limited to bacteremia/sepsis, infectious meningitis, septic arthritis, osteomyelitis, complicated pneumonia, or visceral abscess, which may or may not result in hospitalization during a treatment period. This list is not intended to be all inclusive and the investigator is expected to apply his/her judgement on continuing IMP based on the clinical situation.

However, if a significant infective episode is reported during observation and no treatment with rozanolixizumab period, the decision to start a new treatment cycle should be based on careful evaluation by the Principal Investigator of the Benefit-Risk for the individual study participant and provided a full recovery from infection, an acceptable level of total IgG ($\geq 2\text{g/L}$) and no other discontinuation criteria were met.

4. Study participant meets potential drug-induced liver injury (PDILI) permanent discontinuation criteria.
5. Study participant has a TB test that is confirmed positive or any further evidence suggestive of potential TB infection (ie, exposure) and further examinations result in a diagnosis of active TB or latent TB infection (LTBI).
6. If a nontuberculosis mycobacterium infection (NTMBI) is identified during a study, the same withdrawal procedures as those used for an active TB infection identified during the study should be followed.
7. Removed.
8. Study participant has an AE of severe or serious infusion or anaphylactic reaction requiring corticosteroid and/or epinephrine therapy (Sampson et al, 2006).

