10.6 Appendix 6: Liver Safety – Suggested Actions and Follow-up Assessments

Participants with potential drug-induced liver injury must be assessed to determine if study medication must be discontinued. In addition, all concomitant medications and herbal supplements that are not medically necessary should also be discontinued.

Investigators should attempt to obtain information on study participants in the case of study medication discontinuation to complete the final evaluation.

Study participants with potential drug-induced liver injury should not be withdrawn from the study until investigation and monitoring are complete. All results of these evaluations and observations, as well as the reason(s) for study medication discontinuation and/or participant withdrawal (if applicable), must be recorded in the source documents. The CRF must document the primary reason for discontinuation of study medication.

A specific monitoring plan must be agreed between the UCB Study Physician and the Investigator for study participants who have ALT >5 ULN. The monitoring plan should include any necessary follow-up assessments (until resolution of the abnormal lab values).

Phase 3-4 liver chemistry stopping criteria are designed to assure participant safety and to evaluate liver event etiology.

Phase 3-4 liver Chemistry Stopping Criteria and Follow-Up assessments

Liver Chemistry Stopping Criteria	
ALT-absolute	ALT \geq 8xULN
ALT Increase	ALT \geq 5xULN but $<$ 8xULN persists for \geq 2 weeks ALT \geq 3xULN but $<$ 5xULN persists for \geq 4 weeks
Bilirubin^{a,b}	ALT \geq 3xULN and bilirubin \geq 2xULN ($>$ 35% direct bilirubin)
INR^b	ALT \geq 3xULN and INR $>$ 1.5, if INR measured
Cannot Monitor	ALT \geq 5xULN but $<$ 8xULN and cannot be monitored weekly for \geq 2 weeks ALT \geq 3xULN but $<$ 5xULN and cannot be monitored weekly for \geq 4 weeks
Symptomatic^c	ALT \geq 3xULN associated with symptoms (new or worsening) believed to be related to liver injury or hypersensitivity
Suggested Actions and Follow up Assessments	
Actions	

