
• Immediately discontinue study medication.• Report the event to the UCB within 24 hours.• Complete the liver event CRF, and complete an SAE data collection tool if the event also met the criteria for an SAE.^b• Perform liver chemistry follow-up assessments.	
• Viral hepatitis serology^d• Obtain INR and recheck with each liver chemistry assessment until the transaminases values show downward trend• Only in those with underlying chronic hepatitis B at study entry (identified by positive hepatitis B surface antigen),

Liver Chemistry Stopping Criteria	

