
 Monitor the participant until liver chemistry test abnormalities resolve, stabilize, or return to baseline (see MONITORING). Do not restart/rechallenge participant with study medication unless allowed per protocol and UCB approval is granted. If restart/rechallenge not allowed per protocol or not granted, permanently discontinue study medication and continue participant in the study for any protocol specified follow up assessments. Consider the need for a toxicology screening. 
MONITORING:
 
For bilirubin or INR criteria
 
 Repeat liver chemistry tests (include ALT, AST, alkaline phosphatase, bilirubin) and perform liver event follow-up assessments within 24 hours. Monitor participant twice weekly until liver chemistry test abnormalities resolve, stabilize, or return to baseline. A specialist or hepatology consultation is recommended. 
For all other criteria
 
 Repeat liver chemistry tests (include ALT, AST, alkaline phosphatase, bilirubin) and perform liver chemistry follow-up assessments within 24 to 72 hours. Monitor participants weekly until liver chemistry abnormalities resolve, stabilize, or return to baseline. 	
 quantitative hepatitis B DNA and hepatitis delta antibody^e Obtain blood sample for pharmacokinetic (PK) analysis after the most recent dose^f Serum CPK and LDH Fractionate bilirubin, if total bilirubin $\geq 2 \times \text{ULN}$ Obtain complete blood count with differential to assess eosinophilia Record the appearance or worsening of clinical symptoms of liver injury (eg, fatigue, nausea, vomiting, right upper quadrant pain), or hypersensitivity, on the AE report form Record use of concomitant medications (including acetaminophen, herbal remedies, and other over-the-counter medications) on the concomitant medications CRF. Record alcohol use on the liver event alcohol intake CRF Exclude pregnancy 
For bilirubin or INR criteria:
 
 Antinuclear antibody, antismooth muscle antibody, Type 1 anti-liver kidney microsomal antibodies, and quantitative total IgG or gamma globulins. A serum acetaminophen adduct assay for assessing the potential acetaminophen contribution to liver injury in participants with definite or likely acetaminophen use in the preceding week. Liver imaging (ultrasound, magnetic resonance, or computerized tomography) and/or liver biopsy to evaluate liver disease; complete Liver Imaging and/or Liver Biopsy CRFs.

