Phase 3-4 Liver Chemistry Increased Monitoring Criteria with Continued Study medication

Liver Chemistry Increased Monitoring Criteria	
Criteria	Actions

ALT \geq5xULN and <8xULN and bilirubin <2xULN without symptoms believed to be related to liver injury or hypersensitivity, and who can be monitored weekly for 2 weeks.
 
OR
 
ALT \geq3xULN and <5xULN and bilirubin <2xULN without symptoms believed to be related to liver injury or hypersensitivity, and who can be monitored weekly for 4 weeks.
	
 Notify the Sponsor Medical Monitor medical monitor within 24 hours of learning of the abnormality to discuss participant safety. Participant can continue study medication Participant must return weekly for repeat liver chemistry tests (ALT, AST, alkaline phosphatase, bilirubin) until the abnormalities resolve, stabilize, or return to baseline. If at any time, the participant meets liver chemistry stopping criteria, proceed as described in Section 7.1.1. If ALT decreases from ALT \geq5xULN and <8xULN to \geq3xULN but <5xULN, continue to monitor liver chemistries weekly. If, after 4 weeks of monitoring, ALT <3xULN and bilirubin <2xULN, monitor participants twice monthly until liver chemistry tests resolve, stabilize, or return to baseline.

ALT=alanine aminotransferase; AST=aspartate aminotransferase; ULN=upper limit of normal

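### For a result that meets a liver stopping criterion, Protocol Section 7.1.1 leaves the stop to the Investigator, Appendix 6 orders it at once, and Section 7.1.4 criterion 4 relies on criteria not defined under that name

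*Protocol*

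**What the plan says.** **Protocol Section 7.1.1** is titled as the liver stopping criteria. It reads "Discontinuation of study treatment for abnormal liver function should be considered by the Investigator when a participant meets one of the conditions outlined" in Figures 7-1 and 7-2, or when the Investigator believes stopping is in the participant's best interest. It then adds "Treatment with study medication may be continued with increased monitoring if a study participant meets one of the criteria outlined in" Figure 7-2, and refers to Appendix 6 for assessments and follow-up actions.

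**Protocol Appendix 6 (Section 10.6)** is titled with "Suggested Actions and Follow-up Assessments". It opens with "Participants with potential drug-induced liver injury must be assessed to determine if study medication must be discontinued". Its stopping table has six rows: ALT absolute (≥8×ULN), ALT increase, bilirubin, INR, cannot monitor, and symptomatic. The actions listed below them begin "Immediately discontinue study medication" and include "Do not restart/rechallenge participant with study medication unless allowed per protocol and UCB approval is granted". The text that follows makes discontinuation of study medication permanent if restart is not allowed by the protocol or not granted, and keeps the participant in the study for follow-up. The separate monitoring table says "If at any time, the participant meets liver chemistry stopping criteria, proceed as described in Section 7.1.1".

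**Protocol Section 7.1.4, criterion 4**, in the list of events that oblige permanent discontinuation, reads "Study participant meets potential drug-induced liver injury (PDILI) permanent discontinuation criteria". It gives no cross-reference.

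**Protocol Appendix 2, Table 10-1, note a** points to Section 7.1.1 and Appendix 6 together and describes the actions there as required, not suggested.

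**The concern.** A stopping rule for liver injury should tell every site the same thing. Here the section that carries the rule uses permissive wording, the appendix it points to gives an order, and the appendix's monitoring table points back to the permissive section. The section that makes a permanent stop compulsory names a set of criteria that cannot be found under that name.

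Two things depend on this. The first is participant safety: whether a participant who meets a stopping criterion receives further infusions. The second is classification. TEAEs leading to withdrawal of IMP are one of the two primary safety endpoints (Protocol Section 3; SAP Section 2.2.1.1), and SAP Section 8.2.2 tabulates permanent and temporary withdrawal of IMP separately. If the category depends on which section a site followed, the count partly reflects how the protocol was read.

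**Working it through.** There is no figure to reproduce, so this is a comparison of text. The test case is a participant with ALT ≥8×ULN, the first row of the Appendix 6 stopping table.

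| Place | Instruction for this result | Force |
|---|---|---|
| Section 7.1.1 | Investigator to consider stopping | Discretionary |
| Appendix 6, actions | Stop at once; permanent unless restart is both allowed by the protocol and approved by the sponsor | Worded as an order, but labelled as suggested |
| Table 10-1, note a | Refers to the actions in both places | Called required |
| Appendix 6, monitoring table | A monitored participant who reaches a stopping criterion goes to Section 7.1.1 | Returns to the discretionary text |
| Section 7.1.4, criterion 4 | Permanent stop if PDILI permanent discontinuation criteria are met | Mandatory, criteria not identified |

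**Step 1: discretionary or mandatory.** Row 1 permits continued dosing and row 2 does not. The cross-references run in a circle: 7.1.1 sends the site to Appendix 6, and the monitoring table sends it back. For contrast, the neighbouring QTc rule in Section 7.1.2 states outright that a participant who meets its criteria comes off study medication.

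**Step 2: does Appendix 6 allow a restart?** It sets two conditions, protocol permission and sponsor approval. No section permits or forbids liver rechallenge. Section 7.1.3, which gives the temporary holds and their restart conditions, lists low IgG, COVID-19, suspected drug-induced aseptic meningitis and infection, but no liver event. The protocol condition is therefore not shown to be met, and the Appendix 6 default of permanent discontinuation applies. That is silence, however, and not a stated prohibition.

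**Step 3: what does criterion 4 point to?** The nearest protocol list is the Appendix 6 stopping table, but it has a different name, and treating the two as the same is an assumption. The list that the SAP calls laboratory criteria for pDILI (SAP Section 8.3.1) is a tabulation rule. Each of its three entries needs AST or ALT ≥3×ULN together with raised bilirubin (≥1.5×ULN or ≥2×ULN). Isolated ALT ≥8×ULN would meet criterion 4 under the first list and not under the second. The text does not settle which is meant.

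**Step 4: where the passages agree.** For ALT ≥3×ULN and <8×ULN that meets the monitoring criteria (bilirubin <2×ULN, no relevant symptoms, weekly monitoring possible), Section 7.1.1 and Appendix 6 both allow continued dosing. The conflict is confined to results that meet a stopping criterion.

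**Step 5: consequence in one cycle.** In the initial cycle (Protocol Table 1-2), doses fall on Days 1, 8, 15, 22, 29 and 36, and serum chemistry is drawn on Day 22. If the Day 22 result comes back at ALT ≥8×ULN after that day's dose, 6 − 4 = 2 infusions remain, on Days 29 and 36. A site following 7.1.1 alone may give both, and the event is then no withdrawal of IMP. A site following Appendix 6 gives neither and, on the default in Step 2, records a permanent withdrawal of IMP. This assumes that the result is reported as a TEAE.

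**The case against.** **Section 7.1.1 should not be read alone.** It refers to Appendix 6, and note a of Table 10-1 treats the two together and calls the actions required. A careful site would probably stop. That lowers the chance of divergence, but it does not remove the permissive sentence, the label on the Appendix 6 actions, or the reference back to 7.1.1.

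**A reader might infer three mutually incompatible rules:** consider stopping, stop with possible restart, and stop permanently. The documents do not support that. Appendix 6 itself defaults to permanent discontinuation, and no section opens a liver restart route, so Appendix 6 and Section 7.1.4 largely lead to the same end. The firm conflict is between 7.1.1 and Appendix 6.

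**A reader might infer that sites have no liver criteria to apply.** They do: Appendix 6 gives explicit thresholds. What is missing is the link from criterion 4 to them.

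**A reader might infer that Section 7.1.1 is wrong to name Figure 7-2 as grounds to consider stopping.** Figures 7-1 and 7-2 are not available in the text reviewed. Figure 7-2 may contain its own exit to stopping, as the Appendix 6 monitoring table does, so no point is made of it. Firmer wording in Figure 7-1 would contradict the sentence in 7.1.1, not delete it.

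**The effect on the analysis may be small.** All analyses are descriptive (SAP Section 4.6), and SAP Section 8.3.1 tabulates liver elevations from laboratory values whatever the dosing decision, so the laboratory signal is kept. Appendix 6 also requires a report to the sponsor within 24 hours and an agreed monitoring plan above 5×ULN. These points stand as limits on size. They do not tell a site whether to give the next infusion.

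**Conclusion.** The plan is inconsistent as written. For a result that meets a liver stopping criterion, Section 7.1.1 makes stopping discretionary, Appendix 6 makes it immediate and by default permanent, and Section 7.1.4 criterion 4 mandates a permanent stop on criteria that the visible text does not define under that name. The same qualifying result could lead to continued dosing at one site and permanent discontinuation of study medication, with study follow-up continuing, at another.

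The discretionary-versus-immediate conflict covers all six rows of the Appendix 6 stopping table. How many of those rows criterion 4 covers, if any, cannot be determined. The number of participants affected cannot be given, because the documents state no expected rate of liver events.

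The conclusion rests on the text of these sections without Figures 7-1 and 7-2. It does not extend to lower ALT elevations under monitoring, and it takes no view on which of the conflicting rules is right.

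**What to change.** Reconcile Section 7.1.1, Section 7.1.4 criterion 4 and Appendix 6:

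- Give each row of the Appendix 6 stopping table one action, and word Section 7.1.1 to match it.
- Have criterion 4 cite the rows it means.
- State whether this protocol allows liver rechallenge.
- Settle whether the actions are suggested or required, in both Appendix 6 and note a of Table 10-1.
- Make the monitoring table's reference back to Section 7.1.1 lead to the reconciled instruction.

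The sponsor decides which action belongs to each row and how Section 7.1.1 uses its figures.

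The cost is a protocol clarification. It adds no tests, visits or data collection.
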